**Table 3 Comparison of in Vitro Potencies of MGA012 and Nivolumab and Pembrolizumab Replicas**

[figure not shown]
Property	EC 50 (or IC 50 ) Values (µg/mL) a		
	Mean ± SEM		
	MGA012	Nivolumab replica	Pembrolizumab replica
Binding to PD-1-expressing NS0/PDCD1 cells	0.138 ± 0.046	0.158 ± 0.058	0.140 ± 0.048
Inhibition of sPD-L1 binding to PD-1 expressing NS0/PDCD1 cells	0.010 ± 0.001	0.016 ± 0.005	0.014 ± 0.001
Inhibition of sPD-L2 binding to PD-1 expressing NS0/PDCD1 cells	0.021 ± 0.001	0.028 ± 0.004	0.028 ± 0.003
Inhibition of PD-1/PD-L1 Signaling in luciferase reporter assay	0.090 ± 0.008	0.171 ± 0.017	0.103 ± 0.016

a EC50, effective concentration at 50% of maximal activity; IC50, effective concentration at 50% inhibition of activity.

To support the cynomolgus monkey as a relevant species for nonclinical toxicology evaluation of MGA012, several in vitro pharmacology studies were performed to evaluate MGA012 binding to cynomolgus monkey target antigens and cells as well as its biological activity in this model system. MGA012 was shown to bind cynomolgus PD-1 though at an approximately 6-fold lower binding affinity than human PD-1 (KD values of 3.6 and 0.6 nM for monkey and human PD-1, respectively). MGA012 also bound to both cynomolgus and rhesus monkey PBMCs induced by SEB stimulation. MGA012 did not bind to PD-1 protein from non-primate species (mouse, rat or dog).

Consistent with its specific binding properties and designed mechanism of action, MGA012 blocked the binding of the ligands PD-L1 and PD-L2 to cell surface-expressed PD-1 in a dose-dependent manner (**Figure 7**). MGA012 blocked the PD-1/PD-L1 and PD-1/PD-L2 interactions with mean IC50 values of 0.010 µg/mL and 0.021 µg/mL, respectively. These IC50 values were comparable to those observed with the replicas of nivolumab and pembrolizumab, demonstrating that the in vitro potency of MGA012 is similar to those of the nivolumab and pembrolizumab replicas.

[figure not shown]
**Figure 7 MGA012-mediated Inhibition of Soluble PD-L1 or PD-L2 Binding to a PD-1-positive Cell Line (NS0/PDCD1)**

**Representative dose-inhibition curves of anti-PD-1 mAbs blocking sPD-L1 (A) or sPD-L2 (B) binding to PD1-expressing NS0 cells (NS0/PDCD1). Unlabeled anti-PD-1 mAbs, including nivolumab replica (red line), pembrolizumab replica (blue line), or MGA012 (purple line), were prepared in 1:4 serial dilutions (starting at 10 µg/mL) and incubated with NS0/PDCD1 cells containing 0.1 µg of sPD-L1 or sPD-L2. Total sPD-L1 or sPD-L2 binding (open red circles) and background (open black circle) is shown as positive and negative ligand binding controls. Anti-PD-1 mAb binding was detected with a secondary-labeled goat anti-human Fc-APC conjugate. Data shown are plotted as MFI (APC) by anti-PD1 mAb concentration. Mean EC50 values from multiple experiments are summarized in Table 3.**

MGA012 was evaluated for its ability to directly inhibit the PD-1/PD-L1 inhibitory axis through the use of a co-culture reporter assay system (9). In this system, the functional disruption of PD-1/PD-L1 mediated blockade of nuclear factor of activated T-cells signaling mediated by TCR stimulation is determined in the context of the co-culture of two cell lines: (1) NFAT-luc2/PD-1 Jurkat cells, a reporter cell line which is CD3-positive and engineered for luciferase expression controlled by an NFAT promoter triggered by TCR activation and constitutive PD-1 expression and (2) CHO-PD-L1, a stimulator cell line that stably expresses PD-L1 and a TCR activator (anti-CD3). When co-cultured, NFAT signaling (despite TCR engagement) is strongly inhibited by the PD-1/PD-L1 interaction present between the NFAT-luc2/PD-1 Jurkat cells and CHO-PD-L1 cell lines. In the presence of blocking anti-PD-1 or anti-PD-L1 mAbs, this inhibitory axis is repressed in a dose-dependent manner allowing increased NFAT signaling resulting in luciferase gene expression that is measured optically. As shown in Figure 8, MGA012 blocked the PD-1/PD-L1 inhibitory axis and increased luciferase expression in a dose-dependent manner. The mean EC50 for the increase in luciferase expression resulting from MGA012-mediated inhibition of PD-1/PD-L1 signaling was 0.090 µg/mL, a value comparable to those observed using the replicas of nivolumab and pembrolizumab.

**Figure 8 MGA012-mediated PD-1/PD-L1 Inhibitory Signaling as Measured by Luciferase Gene Expression within a Co-culture Reporter Assay System**

[figure not shown]
Representative evaluation of anti-PD-1 mAbs to enhance luciferase expression by releasing the inhibitory PD-1/PD-L1 axis within a co-culture reporter assay system (Promega). Unlabeled anti-PD-1 mAbs, including nivolumab replica (red line), pembrolizumab replica (blue line), or MGA012 (purple line), were prepared as 1:5 serial dilutions (starting at 20 nM) and incubated in co-culture with Jurkat reporter cells expressing PD-1 and CD3/TCR (NFAT-luc2/PD-1 Jurkat cells) and CHO stimulator cells expressing PD-L1 and a TCR activator (CHO-PD-L1 cells). Release of PD-1/PD-L1-mediated inhibition is measured by an increased luminescence under the control of TCR-mediated NFAT signaling in the presence of anti-PD-1 mAbs. The optical density of each well in duplicate is read at 450nm with luminescence relative light unit (RLU) as the readout. The data were plotted as mean RLU against concentration and fitted using a log (agonist) vs. response-variable slope (four parameter) function. Mean EC50 values from multiple experiments are summarized in Table 3.

MGA012 was evaluated functionally for its ability to enhance the secretion of cytokine IFN- $\gamma$  following stimulation of human PBMCs by SEB. Human PBMCs were stimulated with SEB for 48 hours to induce/increase the expression of PD-1 on T cells, which was confirmed by flow cytometry. The majority of cells expressing PD-1 following SEB stimulation were CD3+ T cells. However, expression of PD-1 was also detected on a subset of CD19+ B cells and CD56+ natural killer (NK) cells. Following the initial SEB stimulation, PBMCs were washed and re-stimulated with SEB in the presence of serially-diluted anti-PD-1 mAbs, and after 2 days, the levels of secreted IFN- $\gamma$  were measured. Enhanced IFN- $\gamma$  secretion was observed across all 8 human donor PBMCs evaluated; representative data with two donors are shown in Figure 9. All donors demonstrated enhanced IFN- $\gamma$  secretion following anti-PD-1 mAb incubation compared to human IgG isotype control, and with 7 of 8 donor PBMCs, MGA012 demonstrated enhanced or comparable IFN- $\gamma$  secretion to the nivolumab and pembrolizumab replicas.

In summary, the data from these in vitro pharmacology studies demonstrate that MGA012 binds to its target, PD-1, and is functional in disrupting the PD-1 PD-L1/L2 inhibitory axis.

Moreover, the biological activities of MGA012 were comparable in potency to those observed with the replicas of pembrolizumab and nivolumab, which were evaluated as reference molecules.

**Figure 9 Evaluation of MGA012 to Enhance IFN- $\gamma$  Signaling Following SEB Stimulation of Human PBMCs**

Secretion of IFN- $\gamma$  from SEB-stimulated human PBMCs (showing 2 representative donors of 8). Human PBMCs were stimulated for 2 days, washed twice, and restimulated with 0.5 ng/mL SEB in the presence or absence of anti-PD-1 mAbs: MGA012, nivolumab replica (AEX1197), pembrolizumab replica (AEX1198). Human PBMCs either cultured alone in media or restimulated with SEB alone or SEB incubated with human IgG isotype control served to establish basal levels of IFN- $\gamma$  secretion. The secretion of IFN- $\gamma$  was determined by ELISA. The optical density of each well was read at 450 nm with luminescence relative light unit (RLU) as the readout and converted by standard curve linear regression to a concentration (pg/mL).

Secondary pharmacodynamic properties of MGA012 were also evaluated, including the ability of MGA012 to mediate ADCC or CDC, to induce cellular proliferation, and to bind to/lyse red blood cells. Consistent with an IgG4-based antibody, MGA012 did not mediate ADCC activity against PD-1 expressing NS0/PDCD1 cells or activated primary human T cells. Consistent with the inability of the IgG4 Fc to bind C1q, MGA012 also did not mediate CDC activity. MGA012 treatment did not induce resting PBMCs to proliferate after 2 days of incubation, demonstrating the lack of intrinsic mutagenicity. The absence of mitogenic effect was also observed with the nivolumab or pembrolizumab replicas. Lastly, given that the planned route of administration for MGA012 in the clinic is by intravenous infusion, MGA012 was tested to ensure that it had no hemolytic properties. No hemolysis was

observed following treatment of either purified red blood cells (RBCs) or whole blood from healthy human donors with MGA012 in vitro.

MGA012-mediated cytokine production was evaluated in vitro with freshly isolated, non-stimulated PBMCs from normal human donors incubated for 24 hours with soluble MGA012 or plate-immobilized MGA012 by wet- or dry-coating. Upon exposure of PBMCs to MGA012 concentrations of 10 µg/mL and 100 µg/mL (i.e., 10-200 times higher than the positive control antibody OKT3), no cytokine production (IFN-γ, TNF-α, IL-2, IL-4, IL-6, and IL-10) was observed with all three conditions of MGA012 presentation.

## 2.5.2 MGA012 Pharmacokinetics and Toxicology

A summary of the nonclinical PK and toxicology data with MGA012 are provided below. Please reference the MGA012 Investigator's Brochure for more detailed descriptions.

The nonclinical toxicology program for MGA012 was performed exclusively in the cynomolgus monkey. The cynomolgus monkey was selected as the most appropriate animal model for nonclinical safety evaluation of MGA012 given the high degree of homology (96%) of the cynomolgus monkey and human PD-1 protein sequences, the ability of MGA012 to bind human and monkey PD-1 protein with similar affinity (within 6-fold), and to bind to human and monkey PBMCs following stimulation of PD-1 expression with SEB. In addition, PD-1 expression detected by the antigen binding regions in MGA012 appears to be similar in monkeys and humans as indicated by the fact that the murine mAb precursor to MGA012, which shares the same antigen specificity as MGA012, demonstrated a similar immunohistochemistry staining profile on lymphocytes in lymphoid organs from monkeys as the staining profile observed with MGA012 in lymphoid organs from humans. Non-primate species (mouse, rat, dog) were not relevant for toxicology studies due to reduced PD-1 protein sequence conservation and lack of detectable MGA012 binding to the PD-1 proteins from these species.

In a GLP tissue cross reactivity study performed on a panel of normal human tissues, MGA012 staining was observed in the membrane and cytoplasm of lymphocytes in germinal centers of lymphoid organs (lymph node, spleen, and tonsil); in medulla of thymus; in submucosal lymphoid aggregates in several human tissues including colon, esophagus, small intestine, kidney, ureter, cervix, uterus and lung; and in tissues where lymphocytes were present including kidney and prostate. This staining was expected based on literature reports of PD-1 expression on T cells in lymphocytes (2, 20, 38, 53). No unexpected tissue staining was observed with MGA012.

A repeat-dose GLP toxicology study of MGA012 was conducted in which MGA012 was administered at dose levels of 0 (saline control), 10, 40 or 150 mg/kg to cynomolgus monkeys (n = 5/sex/group) by 1-hour IV infusions on a once weekly schedule for a total of 4 weeks, which was followed by a 10-week recovery period.

All of the infusions were well tolerated. There were no preterm deaths nor treatment-related toxicities. There were no MGA012-related observations for the following parameters: clinical

signs, body weights, food consumption, physical examinations, ophthalmology, body temperature, blood pressure, heart rate, respiration rate, neurological examinations, electrocardiograms (ECGs), clinical chemistry, coagulation, gross pathology and organ weights.

The only findings related to MGA012 were modest decreases in lymphocytes after the first infusion and microscopic changes at the IV administration site.

Compared to pre-study values, mean absolute lymphocyte counts were moderately decreased (by 40-55%) at 23 hours after the 1st infusion in males and females treated at doses  $\geq 10$  mg/kg (statistically significant for males at 10 and 40 mg/kg and females at 40 and 150 mg/kg compared to controls). Lymphocyte counts returned to near pre-study levels prior to the second infusion but were mildly decreased (by 32-53%) for some individual males and females at all dose levels at 23 hours after the 2nd infusion. Lymphocyte counts increased prior to the 3rd and 4th infusions but decreased (by 45-74%) for some individual males and females at 23 hours post infusion. These modest changes in lymphocyte counts in MGA012-treated animals were mirrored by comparable fluctuations in total circulating leukocytes, T cells (both CD4+ and CD8+), B cells and NK cells, as measured by flow cytometry of peripheral blood. However, there were no changes in circulating monocytes.

Microscopic changes at the IV administration site, observed at 3 days after the last dose, consisted of minimal multifocal perivascular mononuclear cell infiltrates within the superficial dermis (males at  $\geq 40$  mg/kg; females at  $\geq 10$  mg/kg). This finding is an expected reaction to repeated injection of an exogenous protein (monoclonal antibody). No MGA012-related microscopic changes at the IV administration site were noted at 10 weeks post dosing in recovery animals.

Other microscopic changes were of uncertain relationship to MGA012 because of sporadic (non-dose-related) incidence, or because they were also noted in control animals but were noted at a higher incidence and/or severity in MGA012-treated animals. These findings included: minimal to mild perivascular mononuclear cell infiltrates present in the brain (meninges and/or choroid plexus; control and MGA012-treated), spinal cord (MGA012-treated), and urinary bladder (control and MGA012-treated); minimal mixed-cell infiltrates in adipose associated with thyroid gland (MGA012-treated), heart (control and MGA012-treated), and trachea (MGA012-treated); and minimal to mild mononuclear cell inflammation in the wall of the rectum (MGA012-treated). These diffuse patterns of immune cell infiltration were similar to those observed in the repeat-dose toxicology studies with the approved anti-PD1 antibodies, pembrolizumab at 6, 40 or 200 mg/kg and nivolumab at 1, 10, or 50 mg/kg, in cynomolgus monkeys (**FDA BLA 125514 pembrolizumab; FDA BLA 125554 nivolumab 2014**).

Serum cytokine levels were not evaluated in the GLP toxicology study based on the lack of MGA012-related cytokine responses in two prior non-GLP studies, with the single exception of one animal at one time point. No cytokines (IFN- $\gamma$ , IL-2, IL-4, IL-5, IL-6, IL-10, and TNF- $\alpha$ ) were induced in serum samples of cynomolgus monkeys treated with MGA012 following a single dose IV infusion of 10 mg/kg MGA012. Similarly, no cytokines were induced in serum samples of monkeys treated once weekly for 3 weeks with MGA012

administered at 1 or 100 mg/kg, except that one monkey treated at 100 mg/kg had a single significant observed elevation in IL-6 (1946 pg/mL) at 3 hours following the first infusion that resolved by 6 hours (returned to 8 pg/mL) without corresponding clinical effect. It is noted that an elevation in IL-6 of similar magnitude had been observed in a control treated animal in another monkey study.

As can be expected with a humanized protein administered to non-human primates, ADA against MGA012 were detected in several animals after repeat dosing. Evidence of decreased MGA012 serum concentrations following repeated doses of MGA012 were observed in 7/10, 4/10, and 3/10 animals in the 10, 40, and 150 mg/kg dose groups, respectively and the presence of ADA against MGA012 was confirmed in 4, 2, and 1 of the animals in these dose groups, respectively. All the animals in which ADA was not confirmed were in the terminal necropsy group during which MGA012 serum concentrations likely interfered with the ability to detect ADA. Accordingly, data from animals in which ADA appeared to affect MGA012 serum concentrations were excluded from toxicokinetic (TK) evaluations. It is noted that immunogenic responses to humanized therapeutic proteins in cynomolgus monkeys are not generally predictive of immunogenicity in humans; therefore, immunogenicity is expected to be less prevalent in humans.

PK parameters of clearance (CL), volume of distribution at steady state ( $V_{ss}$ ) and mean residence time (MRT) did not vary significantly with dose, hence the PK of MGA012 are linear across the dose range evaluated (10-150 mg/kg). Mean CL by noncompartmental analysis (NCA) ranged from 0.19-0.23 mL/h/kg across the 3 dose groups. CL by two-compartment analysis of data across all 4 cycles, after excluding data after the development of ADA, ranged from 0.21 to 0.24 mL/h/kg. Overall, CL was substantially lower than the glomerular filtration rate in cynomolgus monkeys (~ 125 mL/h/kg), indicating minimal renal clearance as would be expected for a large molecular weight protein (~ 148 kDa). Mean  $V_{ss}$  was 68 mL/kg by NCA analysis of the first dose and 72 mL/kg by two-compartment modeling of data across all cycles for the 3 dose groups. This indicates distribution into a space about 50-60% larger than the plasma space (~ 45 mL/kg), but less than the extracellular space (~ 200 mL/kg) of cynomolgus monkeys, which suggests that MGA012 extravasates from the vascular compartment into tissue extracellular space and/or binding of MGA012 to cells or tissues. For all groups combined, the mean MRT by NCA analysis of the first dose or two-compartment analysis of all cycles was 335 hours or 329 hours, respectively, or approximately 14 days. Based on the two-compartmental modeling, steady-state was predicted to be achieved in the monkeys after 5 weekly doses of MGA012 and the accumulation index was 2.4.

[figure not shown]
MGA012 binds to PD-1 on the surface of CD4+ and CD8+ T cells in cynomolgus monkeys treated with MGA012 and saturation of the binding of MGA012 to PD-1 on T cells was observed at all dose levels during the dosing phase. In animals administered MGA012 at 10, 40 or 150 mg/kg that did not develop ADA responses, serum MGA012 concentrations remained above 29 µg/mL and maximal MGA012 binding to PD-1+/CD4+ T cells and PD-1+/CD8+ T cells was maintained during the entire 10-week recovery period (**Figure 10**). In animals that developed ADA responses, the frequency of MGA012-bound PD-1+ T cells declined to baseline levels and the declines appeared to initiate when the serum MGA012

concentrations dropped below approximately 25 µg/mL. However, it is not known if this apparent threshold relationship applies to ADA-negative animals, since the presence of ADA in ADA-positive animals may contribute to blocking the binding of MGA012 to PD-1.

In summary, administration of MGA012 via 1-hour IV once weekly for 4 weeks was clinically well tolerated in cynomolgus monkeys at levels of 10, 40, or 150 mg/kg. Observed MGA012-related effects were limited to transient decreases in circulating lymphocyte counts and minimal injection-site changes related to injection of a foreign protein. Based on these results, the NOAEL was considered to be 150 mg/kg (gender combined mean  $C_{max}$  of 3.94 mg/mL and AUC of 746 h•mg/mL). The PK parameters for MGA012 were linear across the dose range tested and the mean residence time was approximately 14 days. MGA012, at all dose levels, exhibited durable binding to PD-1-expressing T cells, which persisted for at least 10 weeks post-dosing in the monkeys that did not develop ADA responses.

**Figure 10** Frequency of PD-1+/CD4+ and PD-1+/CD8+ Cells Bound by MGA012 and MGA012 Serum Concentrations in Cynomolgus Monkeys

The percentages of PD 1+/CD4+ and PD-1+/CD8+ cells bound by MGA012 were compared to the serum concentrations of MGA012 for cynomolgus monkeys treated with MGA012 at 10, 40, or 150 mg/kg and followed during the 10-week post-dose recovery period. Percentages of PD 1+/CD4+ cells bound by MGA012 (left panels) and percentages of PD-1+/CD8+ cells bound by MGA012 (right panels) are represented by black squares and the dashed reference lines indicate saturated (100%) binding. Serum MGA012 concentrations are represented by red circles. Data are from representative animals from each dose group that that did not develop anti-drug antibodies (ADA) during the 10-week recovery period. The days of MGA012 dosing are marked by arrows below the x-axis.

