## 4 STUDY DESIGN

### 4.1 Overall Study Design and Plan

[figure not shown]
This study is an open-label, Phase 1b/2 dose escalation and cohort expansion study designed to characterize the safety, tolerability, PK, pharmacodynamics, immunogenicity, and preliminary antitumor activity of MGD007 and MGA012, administered in combination by IV infusion, in patients with histologically proven, relapsed/refractory metastatic colorectal carcinoma, irrespective of the KRAS and MMR status of their tumors. This study will enroll patients as described below.

The study will proceed in 2 distinct phases as follows: Dose Escalation Phase to determine the MTD or MAD (if no MTD is defined) of the combination, followed by a Cohort Expansion Phase to further define the safety and initial antitumor activity of the combination with the doses established in the Dose Escalation Phase.

Patients will be treated with MGD007 and MGA012 as shown in [Figure 11](#). MGD007 will be administered at the target dose for each assigned cohort as an IV infusion over 120 minutes, once weekly (QW), in 8-week treatment cycles. MGA012 will be administered at 3 mg/kg as an IV infusion over 60 minutes, once every 2 weeks (Q2W) beginning on Cycle 1 Day 15, and every 2 weeks thereafter. For each patient, administration of the first dose of MGA012 will occur 2 weeks after the first dosing of MGD007. The DLT evaluation period will last until Cycle 1 Day 42. Disease status will be evaluated on Cycle 1 Day 56 ( $\pm$  3 days) using CT and/or MRI as appropriate for the sites of disease, accompanied by physical examination, and will then be evaluated every 8 weeks while on study treatment. Although response assessment will be performed according to both conventional (RECIST 1.1 [\[Appendix 5\]](#)) and irRECIST ([Appendix 6](#)), patients will be managed according to irRECIST principles. This approach allows for limited treatment of patients beyond the initial radiographic documentation of disease progression, assuming that the Investigator feels that the patients are tolerating therapy adequately, that patients remain otherwise clinically stable despite this initial radiographic evidence of disease progression, and that the Investigator feels the patient may still derive benefit from continuation of therapy.

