## 9.11 End of Treatment Visit

A list of evaluations to be performed for the EOTV is provided in [Appendix 1](#); a CT or MRI Scan should be performed during the EOTV, unless a previous scan was performed < 28 days of the EOTV. Criteria for triggering the End of Treatment visit are specified in [Section 5.4](#).

The End of Treatment Visit should be performed after the patient has met off-study criteria. This visit should occur no later than 30 days since the last study dose and before any subsequent anti-cancer treatment. If EOTV < 30 days since the last study dose, the site should contact the patient for safety follow-up no later than 30 days after the last study dose (see [Section 12](#)). It is recognized that certain patients (such as those experiencing progression of disease) may be cared for in facilities other than the participating study site, may proceed to receive other cancer therapy, and/or may elect not to return to the study site. Therefore, this visit is considered optional, but should be carried out whenever possible. All required procedures and tests should be performed if a visit is performed.

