### **Appendix 3      Pharmacokinetics, Immunogenicity, and Pharmacodynamic Biomarkers Blood Sampling Schedule for MGD007 & MGA012**

Blood samples for MGD007 and MGA012 PK, ADA, and PD biomarkers will be collected per [Table 15](#).

**Table 15 Pharmacokinetic, Immunogenicity, and Pharmacodynamic Biomarkers Blood Sampling Schedule for MGD007 & MGA012 **

Cycle	Day	MGD007 & MGA012 PK Sampling Time 	MGD007 & MGA012 ADA Sampling Time	Cytokines 	Flow Cytometry Occupancy	Flow Cytometry Subsets	Serum Bio-markers 	T-cell repertoire 	ctDNA analysis 	Transcript profile 
1	1	Pre MGD007 infusion	Pre MGD007 infusion	Pre MGD007 infusion	Pre MGD007 infusion	Pre MGD007 infusion	Pre MGD007 infusion	Pre MGD007 infusion	Pre MGD007 infusion	Pre MGD007 infusion
	1	End of MGD007 infusion								
	1	2 hours after end of MGD007 infusion		2 hours after end of MGD007 infusion	2 hours after end of MGD007 infusion	2 hours after end of MGD007 infusion				
	1	6 hours after end of MGD007 infusion		6 hours after end of MGD007 infusion						
1	2			Day 2	Day 2	Day 2				
1	8	Pre MGD007 infusion			Pre MGD007 infusion	Pre MGD007 infusion	Pre MGD007 infusion			
	8	End of MGD007 infusion								
	8				2 hours after end of MGD007 infusion	2 hours after end of MGD007 infusion				
1	15	Pre MGA012 infusion	Pre MGA012 infusion	Pre MGA012 infusion	Pre MGA012 infusion	Pre MGA012 infusion	Pre MGA012 infusion			

**Table 15 Pharmacokinetic, Immunogenicity, and Pharmacodynamic Biomarkers Blood Sampling Schedule for MGD007 & MGA012 **

Cycle	Day	MGD007 & MGA012 PK Sampling Time 	MGD007 & MGA012 ADA Sampling Time	Cytokines 	Flow Cytometry Occupancy	Flow Cytometry Subsets	Serum Bio-markers 	T-cell repertoire 	ctDNA analysis 	Transcript profile 
1	15	End of MGA012 infusion								
	15	End of MGD007 infusion								
	15				2 hours after end of MGD007 infusion	2 hours after end of MGD007 infusion				
	15	1 hour after end of MGD007 infusion								
	15	2 hours after end of MGD007 infusion								
	15	4 hours after end of MGD007 infusion								
	15			6 hours after end of MGD007 infusion						
1	16	Day 16		Day 16	Day 16	Day 16				
1	17	Day 17								
1	19	Day 19								

**Table 15 Pharmacokinetic, Immunogenicity, and Pharmacodynamic Biomarkers Blood Sampling Schedule for MGD007 & MGA012 **

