Cycle	Day	MGD007 & MGA012 PK Sampling Time 	MGD007 & MGA012 ADA Sampling Time	Cytokines 	Flow Cytometry Occupancy	Flow Cytometry Subsets	Serum Bio-markers 	T-cell repertoire 	ctDNA analysis 	Transcript profile 
1	22	Pre MGD007 infusion				Pre MGD007 infusion				
	22	End of MGD007 infusion				End of MGD007 infusion				
1	29	Pre MGA012 infusion	Pre MGA012 infusion	Pre MGA012 infusion	Pre MGA012 infusion	Pre MGA012 infusion	Pre MGA012 infusion			
	29	End of MGA012 infusion								
	29	End of MGD007 infusion			End of MGD007 infusion	End of MGD007 infusion				
	29			2 hours after end of MGD007 infusion						
1	42							Pre Biopsy	Pre Biopsy	Pre Biopsy
1	43	Pre MGA012 infusion								
	43	End of MGA012 infusion								
	43	End of MGD007 infusion								

**Table 15 Pharmacokinetic, Immunogenicity, and Pharmacodynamic Biomarkers Blood Sampling Schedule for MGD007 & MGA012 **

Cycle	Day	MGD007 & MGA012 PK Sampling Time 	MGD007 & MGA012 ADA Sampling Time	Cytokines 	Flow Cytometry Occupancy	Flow Cytometry Subsets	Serum Bio-markers 	T-cell repertoire 	ctDNA analysis 	Transcript profile 
2	1	Pre MGA012 infusion	Pre MGA012 infusion	Pre MGA012 infusion	Pre MGA012 infusion	Pre MGA012 infusion	Pre MGA012 infusion	Pre MGA012 infusion	Pre MGA012 infusion	
	1	End of MGA012 infusion								
	1	End of MGD007 infusion			End of MGD007 infusion					
	1			2 hours after end of MGD007 infusion						
2	2			Day 2						
2	15	Pre MGA012 infusion								
	15	End of MGA012 infusion								
	15	End of MGD007 infusion								
2	29				Pre MGA012 infusion	Pre MGA012 infusion				
	29				End of MGD007 infusion					

**Table 15 Pharmacokinetic, Immunogenicity, and Pharmacodynamic Biomarkers Blood Sampling Schedule for MGD007 & MGA012 **

Cycle	Day	MGD007 & MGA012 PK Sampling Time 	MGD007 & MGA012 ADA Sampling Time	Cytokines 	Flow Cytometry Occupancy	Flow Cytometry Subsets	Serum Bio-markers 	T-cell repertoire 	ctDNA analysis 	Transcript profile 
3	1	Pre MGA012 infusion	Pre MGA012 infusion			Pre MGA012 infusion	Pre MGA012 infusion	Pre MGA012 infusion	Pre MGA012 infusion	
	1	End of MGA012 infusion								
	1	End of MGD007 infusion								
3	29					Pre MGA012 infusion				
4	1	Pre MGA012 infusion	Pre MGA012 infusion			Pre MGA012 infusion	Pre MGA012 infusion			

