6.8 Pharmacokinetic, Pharmacodynamic, and Immunological Parameter Endpoint Analyses

Pharmacokinetic Analysis: Summary statistics will be tabulated separately for serum PK parameters by MGD007 and MGA012 dose. Geometric means and percent coefficients of variation will be reported for C_{\max} , $AUC_{(0-T)}$, $AUC_{(TAU)}$, $AUC_{(INF)}$, and C_{trough} ; arithmetic means and standard deviations will be reported for $t_{1/2}$, CL, and V_{ss} ; and medians, minimum, and maximum will be reported for T_{\max} . Separate scatter plots of C_{\max} and AUC will be

provided versus dose to assess dose dependency. Dose proportionality may be assessed using a power model. Population PK analyses may be conducted using data from this study alone or combined with data from other studies.

Immunogenicity Analysis: The proportion of patients who are negative for ADA at baseline and become positive in this assay, the proportion of patients who are negative at baseline and remain negative, and those who have positive ADA at baseline that increases or decreases in titer over the course of treatment will be summarized. Analysis will be conducted separately for MGD007 and MGA012.

Pharmacodynamic Analysis: Summary statistics for pharmacodynamic parameters and corresponding changes from baseline will be summarized and/or may also be presented graphically as well as possible associations between changes in pharmacodynamic measures of interest and MGD007 in combination with MGA012 dose and exposure may be explored.

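### MGA012 ADA incidence may be understated, because the plan has no inconclusive category for negatives drawn with MGA012 in serum

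*Protocol*

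**What the plan says.** **Monkey evidence (Protocol 2.5.2).** MGA012 concentrations fell after repeat dosing in "7/10, 4/10, and 3/10 animals in the 10, 40, and 150 mg/kg dose groups", and ADA was "confirmed in 4, 2, and 1 of the animals in these dose groups". All the unconfirmed animals were in the terminal necropsy group. The protocol's explanation is that "MGA012 serum concentrations likely interfered with the ability to detect ADA".

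**Sampling in patients.** Under Protocol 4.1, "administration of the first dose of MGA012 will occur 2 weeks after the first dosing of MGD007", which is Cycle 1 Day 15. In Appendix 3, Table 15, the column headed "MGD007 & MGA012 ADA Sampling Time" lists:
- Cycle 1 Day 1, before MGD007
- Cycle 1 Days 15 and 29, and Day 1 of Cycle 2 and every later cycle, each marked "Pre MGA012 infusion"
- End of Treatment

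A PK sample is scheduled at each of these times. On the End of Treatment visit, Protocol 9.11 says "This visit should occur no later than 30 days since the last study dose". After that, Protocol 9.12 provides only remote contact, so no washout ADA sample exists.

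**Analysis.** Protocol 14.5.2 and SAP 6.8 define three groups, separately for each drug: baseline-negative patients who turn positive, "the proportion of patients who are negative at baseline and remain negative", and baseline-positive patients whose titre changes. Neither section uses the paired drug concentration. Protocol 11.2 says the assay is an ELISA and gives no drug tolerance.

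**The concern.** An ADA assay has a drug concentration above which it can no longer be relied on to detect antibody. A negative drawn above that level says nothing about whether antibody is present, yet the plan files it with the patients who stayed negative. Any resulting error can only lower the reported incidence. The sponsor itself invoked this mechanism for this drug, and the trial repeats the condition at every ADA sample after MGA012 starts. Immunogenicity is a secondary objective in both phases. A low MGA012 ADA rate could be read as absence of antibody, and misfiled negatives would also blur any comparison of drug exposure by ADA status.

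**Working it through.** **Inputs.** MGA012 half-life 408.9 h (Protocol 2.6.2.1). Predicted troughs at 3 mg/kg Q2W: 11.6 µg/mL (CV 9%) after the first dose and 23.6 µg/mL (CV 67%) at steady state, from N = 5 (Table 7). End of Treatment at most 30 days after the last study dose (9.11).

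**1. Reproduce the plan's figures.** Half-life = 408.9/24 = 17.04 days. Five half-lives = 85.2 days, against the stated 85. Q2W accumulation = 1/(1 − 2^(−14/17.04)) = 2.30, and the Table 7 trough ratio is 23.6/11.6 = 2.03; the plan says about 2. The persistence figures hold.

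**2. Predicted MGA012 at each ADA sample.**
- Cycle 1 Day 15: none, because the sample precedes the first MGA012 infusion. Under SAP 6.1 it is nevertheless a post-baseline sample.
- Cycle 1 Day 29: about 11.6 µg/mL.
- Later pre-dose samples: rising to about 23.6 µg/mL.
- End of Treatment, 30 days after a steady-state dose: 23.6 × 2^(−(30 − 14)/17.04) = 12.3 µg/mL. Falling to 1 µg/mL would take 14 + 17.04 × log2(23.6) = about 92 days.

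**3. Share of steady-state troughs above an assumed tolerance T.** The documents do not give T, so a range is shown. Assume a lognormal distribution with geometric mean 23.6 and σ = √ln(1 + 0.67²) = 0.609. The share above T is 1 − Φ(ln(T/23.6)/0.609).

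| Assumed T (µg/mL) | Share above T |
|---|---|
| 5 | 99% |
| 10 | 92% |
| 25 | 46% |
| 50 | 11% |
| 100 | 0.9% |

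The first-dose trough is lower and less variable. By the same method with CV 9%, 95% of Day 29 samples exceed 10 µg/mL but only 0.2% exceed 15.

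**4. What this could do to a reported rate.** Suppose 2 positives among 25 patients, and one steady-state trough per patient. The plan reports 2/25 = 8%.
- T = 100: 23 × 0.009 = 0.2 inconclusive, so no change.
- T = 50: 23 × 0.109 = 2.5, so 2 or 3 inconclusive. The bounds run from 8% to 4/25 = 16% or 5/25 = 20%.
- T = 25: 23 × 0.462 = 10.6, so 11 inconclusive, and 8% to 13/25 = 52%.
- T = 10: 23 × 0.921 = 21.2, so 21 inconclusive, and 8% to 23/25 = 92%.

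Patients with several samples have more chances of an interpretable one, so these ranges are wider than a patient-level analysis would usually give.

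**The case against.** A reader might infer that half of all ADA is missed: 7 + 4 + 3 = 14 animals suspected, 4 + 2 + 1 = 7 confirmed, so a true 20% would appear as 10%. The documents do not support that. Every unconfirmed animal was in the terminal necropsy group, so 7/14 reflects how animals were split between necropsy and recovery and is not an assay detection rate. The 14 had falling concentrations, not proven ADA. The animals received 10 to 150 mg/kg weekly, against 3 mg/kg every two weeks here, and serum levels in the masked animals are not reported.

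A reader might also infer that incidence is in fact understated. That needs the human assay's tolerance. If it is 100 µg/mL or more, the plan's rule does essentially no harm.

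Other points on the plan's side also stand:
- The sections describe results in the assay and do not claim true antibody status.
- SAP Section 7 defers reporting conventions to a programming plan that is not available here.
- Antibody that speeds clearance lowers drug levels and may unmask itself, so loss per patient may be smaller than loss per sample.
- The evidence concerns MGA012 only. The predicted MGD007 steady-state trough at 0.4 µg/kg is 0.41 ng/mL (Table 5).
- SAP 6.1 calls the summaries mostly descriptive, and neither document ties a dose or efficacy decision to ADA incidence.

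These points limit the size and scope of the concern. They do not supply a category for an uninterpretable negative or a reason to leave the paired concentrations unused.

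**Conclusion.** The point holds as a possible downward bias in MGA012 ADA incidence. It affects samples from Cycle 1 Day 29 on and does not affect Cycle 1 Day 15. Its size cannot be fixed from the documents: across assumed tolerances of 100 down to 10 µg/mL, the share of steady-state troughs in doubt runs from about 1% to 92%. This rests on predicted troughs from five patients, a lognormal shape, and decline at the stated half-life. The monkey ratio should not be carried over to patients. The matter is secondary, but the remedy is inexpensive and the present rule cannot show which end of the range applies.

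**What to change.** For the MGA012 ADA analysis in SAP 6.8 and Protocol 14.5.2:

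1. State the assay's validated drug tolerance.
2. Using the paired PK sample in Table 15, class an ADA-negative sample as inconclusive when MGA012 exceeds that tolerance.
3. Call a patient with no positive sample negative only if at least one sample after the first MGA012 dose is negative with drug below tolerance. The Cycle 1 Day 15 pre-dose sample does not count for this.
4. Keep all patients with an ADA sample after the first MGA012 dose in the denominator. Report the number inconclusive, with bounds counting them as all negative and as all positive.
5. Tabulate inconclusive samples by visit, since a clean Day 29 sample comes only two weeks after first exposure and does not speak for later visits.

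Inconclusive patients should not be dropped from the denominator: that keeps every positive and removes negatives, so it selects on outcome. Take 25 patients, a true incidence of 20% and an assumed 50% detection, giving 2.5 positives and 22.5 negatives. With one steady-state trough each and T = 10 µg/mL, about 8% of the negatives (1.8) remain, and the reported rate is 2.5/(2.5 + 1.8) = 58%.

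The cost is a few sentences of text and a merge of PK and ADA data already planned, with no new visit or blood draw. The downside is that some patients become inconclusive and the reported incidence becomes a range.
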